#### Core sample #1 and #2– Nucleic acid changes

##### RNA isolation, probe preparation, and expression microarray: Hybridization –Affymetrix platform

Total RNA will be isolated from tissue using the DNA/RNA all prep kit(Qiagen). Quality of RNA will be ensured before labeling by analyzing 2 to 5 ng of each sample using the RNA 6000 NanoAssay and a Bioanalyzer 2100 (Agilent). Samples with a 28S/18S ribosomal peak ratio of 1.8–2.0 and a RIN number >7.0 will be considered suitable for labeling. For samples meeting this standard, 1 to 2  $\mu$ g of total RNA will be used for cDNA synthesis using an oligo-dT-T7 primer and the SuperScript Double-Stranded cDNA Synthesis Kit (Invitrogen). Synthesis, linear amplification, and labeling of cRNA will be accomplished by in-vitro transcription using the MessageAmp aRNA Kit (Ambion) and biotinylated nucleotides (Enzo Diagnostics). Ten micrograms of labeled and fragmented cRNA will be hybridized to the Human HG-U133A2.0 GeneChip (Affymetrix) at 45 degrees

C for 16 h. Post hybridization staining, washing were processed according to manufacturer (Affymetrix). Finally, chips will be scanned with a high-numerical Aperture and flying objective (FOL) lens in the GS3000 scanner (Affymetrix). The image will be quantified using GCOS 1.4 (GeneChip Operating Software, Affymetrix) with the default parameters for the statistical algorithm and all probe set scaling with a target intensity of 500.

#### Whole exome capture using the Agilent SureSelect platform and Hiseq 2000 sequencing.

DNA capture will be performed on 3 µg of high quality genomic DNA using the 51MB SureSelect Human Exome Target Enrichment kit (Agilent) according to the protocol provided by Agilent. Enriched DNA libraries will then be sequenced on a Hiseq2000 (Illumina), using 75x75 paired end V3 sequencing chemistry. The goal will be to generate 80 to 100 million reads per samples, to reach an average coverage of 100x on 85% of the targeted region.

#### miRNA profiling on Agilent Human miRNA array

The same QC standards will be applied as for the Affymetrix Gene expression platform. Briefly, samples with a 28S/18S ribosomal peak ratio of 1.8–2.0 and a RIN number >7.0 will be considered suitable for labeling. 200 ng of total RNA will be labeled using the miRNA Complete Labeling and Hybridization Kit (Agilent). Labeled RNA will be hybridized for 20hrs at 20 rpm, 55 °C. Slides will be washed and scanned according to manufacturer's instructions. Images will be quantified using Feature Extraction 10.4 (Agilent)

#### **Core #3 and #4: Protein expression changes**

Evaluate changes in protein phosphorylation in pre -treatment and day 8 tumor tissue biopsies. We will utilize Zeptosens technology to facilitate high-throughput profiling of (phospho-) protein levels in tumor tissue. The system is significantly more sensitive, faster and less expensive than Western blots, requiring much smaller protein amounts. The ZeptoMARK reverse protein array system additionally allows measurement of protein expression and post-translational modifications (phosphorylation, methylation etc.) in signaling pathways. Over 300 validated antibodies in various signaling pathways, including Akt, MAPK, lipid, cAMP, insulin and many others, are available for use on ZeptoMARK reverse arrays. Briefly, treated and control tissue material in an equivalent amount are lysed using ZeptoMARK reverse array lysis buffer as per manufacturer's protocol. The denaturing and enzyme inhibiting properties of the lysis buffer allows the biological processes within the cells to be preserved. Frozen lysates can be stored for long periods of time, if necessary. Further processing is carried out using robotic liquid handling equipment existing at MSKCC Core Facility. Lysates are normalized for further processing based on total protein concentrations. Each normalized sample is diluted in a reverse array spotting buffer in a series of four concentrations and then reformatted from 96 to 384 well plates as the source for spotting. Lysates are spotted in duplicates at 4 concentrations on the ZeptoMARK chip using the array spotter. The chips are coated with a proprietary high absorbance surface. Only per lysate are required per spot, an almost unlimited number of replica arrays can be prepared from about 100µl of lysate solution. The chip is then blocked using ZeptoMARK reverse array blocking buffer in the blocking station. Each chip contains 6 arrays that are probed independently with an antibody specifically binding to a signaling protein or its activated form. The fluorescence markers are introduced by application of a labeled anti-species antibody. Only 20 µL of detection antibody (1:250 - 1:10000 dilution of stock solution) is required per array. Surface confined fluorophores are measured at green or red excitation wavelengths in a wet state in the ZeptoREADER. Signal processing of microarray images taken by the ZeptoREADER is performed with the ZeptoVIEW software, and data is then exported in a standard format for further analysis,

for example bioinformatic pathway analysis. We will specifically evaluate changes in Wnt pathway along with the Notch and Hedgehog pathways. Other pathways to interrogate will include the major and minor targets of sorafenib which include VEGFR2/3, PDGFR- $\beta$ , RAF, KIT, CDK5, Ephrin (EPHA1-2, EPHB4) and FGFR. Lastly, we will also consider evaluating total and phosphorylated levels of Akt, p-Akt (S473), p-p70-S6K, PTEN, p-Mek and p-Erk.

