### 10.3.4 A091105-ST1 Biopsies

#### Pre- and day 8 (+ 7 days) post-randomization biopsy guidelines

A091105-ST1 must be offered to all patients enrolled on A091105 (although patients may opt to not participate). Patients who consent to A091105-ST1 will undergo 2 biopsies (pre-treatment and day 8 post-randomization).

The following exploratory studies will be performed and analyzed in the laboratory of [name], correlative chair. Bio-informatics analysis will be provided by MSKCC Bio-informatics core lab. Blood, pre-treatment and day 8 matched tumor biopsies are required elements of this study for patients. Patients will undergo 2 biopsies (procuring 5 cores for each biopsy) by interventional radiology under image guided CT or U/S. Core biopsies will be evaluated for the following studies: 1) one core will be formalin fixed for pathological studies and TMA construction, 2) 1 - 2 cores will be used for gene array expression profiling to determine a sorafenib signature of response, whole exome sequencing, microRNA array and epigenetics 3) one core will be used for a constrained evaluation of phospho-proteomic changes utilizing a Zaptosens reverse protein array of selected pathways identified from genetic studies.

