### 15.3.3 Statistical design for correlative study A091105-ST1

See the note in [Section 15.2](#), which will apply to all analyses for this section A091105-ST1.

Statistics for Core #1: Archival FFPE and TMA studies: Associations among the possible predictors of response to sorafenib and CTNNB1 mutations will be examined using Fisher’s exact test, Kruskal-Wallis test, or Spearman’s correlation coefficient as appropriate. Variables considered include *CTNNB1* genotype, tumor size, tumor site, gender, age at initial diagnosis, and primary versus recurrent disease. Strata will be compared by using the log-rank test. Multivariate models will be constructed by introducing all variables aforementioned simultaneously into the model and then eliminating variables using the backward selection method. *P* values will be two-tailed and considered significant at alpha 0.05. Analyses will be conducted using SAS for Windows (release 9.3; SAS Institute, Cary, NC).

Statistics for Core #2: Microarray: A two-sided t-test will be used to identify differentially expressed genes on log transformed data and those with a twofold change. False discovery rate (FDR) will be assessed by permutation testing ( $n = 1000$ ) of the sample group labels. The selection approach is to first compute two *t*-tests and fold changes for each comparison between pre-treatment and day 8 versus the normal skin biopsy. Genes that have a nominal *p* value < 0.01 and fold > 2 for each comparison will be selected. To assess FDR,

permutation testing of the same selection will be performed 1000 times and the sample group labels switched around in each permutation. Java TreeView color maps will be generated. To unravel a treatment-specific gene expression signature, the analysis will identify over- and under-expressed genes in pre- treatment and day 8 biopsies as compared to all control samples (germlineDNA extracted from whole blood). Using Sigterms, sorafenib associated gene signature will search for Gene Ontology (GO) annotation terms, gene sets curated by the Molecular Signature Database (MSigDB, v2.5 and top enriched transcription factor sequence motifs. Enrichment will be assessed by one-sided Fisher's exact test with estimated FDR.

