Statistics for Core #3 and 4: For each paired sample, differences in protein levels will be compared by paired t-test. This sample size of 75 patients will allow 93% power to detect 1 standardized difference. Quantitative changes in IHC score of VEGF, PDGFR and  $\beta$ -catenin cytoplasm/nuclear ratio will be correlated with disease status at 1 year by Fishers exact test.

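### The ST1 protein comparisons (section 15.3.3, Core #3 and 4) are unadjusted paired t-tests on a panel of unstated size, while the gene array in the same section has an FDR assessment

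*Combined protocol and SAP*

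**What the plan says.** For the protein cores, section 15.3.3 (Core #3 and 4) gives one rule: "For each paired sample, differences in protein levels will be compared by paired t-test". The next sentence gives a power figure: "This sample size of 75 patients will allow 93% power to detect 1 standardized difference". Neither sentence states a significance level, the number of proteins or any multiplicity control.

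The same section treats the other analyses differently:
- Core #1 (archival tissue): P "values will be two-tailed and considered significant at alpha 0.05".
- Core #2 (gene array): genes with nominal p "value < 0.01 and fold > 2 for each comparison will be selected", and "False discovery rate (FDR) will be assessed by permutation testing". The enrichment step that follows also carries an estimated FDR.

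The panel is described in section 10.3.4. The biopsy guidelines speak of a constrained evaluation "utilizing a Zaptosens reverse protein array of selected pathways identified from genetic studies". The Core #3 and #4 text says of the platform that "Over 300 validated antibodies in various signaling pathways, including Akt, MAPK, lipid, cAMP, insulin and many others, are available for use". It then states: "We will specifically evaluate changes in Wnt pathway along with the Notch and Hedgehog pathways". It goes on to name sorafenib targets (VEGFR2/3, PDGFR-beta, RAF, KIT, CDK5, EPHA1-2, EPHB4, FGFR), and finally Akt, p-Akt, p-p70-S6K, PTEN, p-Mek and p-Erk as items to be considered. No closed list is given.

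**The concern.** Objective 2.3.2 and the hypothesis in section 10.3.3 use the paired biopsies to say which pathways sorafenib modulates. The protein results will be read as a list of changed proteins. If each is tested at a nominal level with no account of how many were run, the reader cannot tell how many entries on the list would be expected by chance. The plan deals with this for RNA but not for protein, on a platform that it also describes as high-throughput.

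A second issue concerns labelling. Section 10.3.4 lets genetic results steer which pathways go on the array, and the gene and protein cores come from the same biopsies. A protein change in a pathway chosen that way may be presented as confirming the gene result, although both come from the same patients and samples.

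**Working it through.** **The plan's own figure.** Section 15.3.3 states 93% power with 75 patients for 1 standardized difference. For a paired t-test, power comes from the noncentral t distribution with n - 1 degrees of freedom and noncentrality d x sqrt(n). With n = 75, d = 1 and an assumed two-sided 0.05, the noncentrality is sqrt(75) = 8.66 and power exceeds 99.9%. About 14 pairs already give 93.2%. The stated 93% therefore does not reproduce for the test described, and it cannot be used to infer an intended per-test level or number of tests.

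**Inputs for multiplicity**
- Items named in section 10.3.4: 3 pathways (Wnt, Notch, Hedgehog); 10 sorafenib targets (VEGFR2, VEGFR3, PDGFR-beta, RAF, KIT, CDK5, EPHA1, EPHA2, EPHB4, FGFR); 6 downstream markers (Akt, p-Akt, p-p70-S6K, PTEN, p-Mek, p-Erk). The total is 3 + 10 + 6 = 19, with each pathway counted once.
- Per-test level: not stated for Core #3 and 4. Two-sided 0.05 is assumed, borrowed from Core #1; 0.01 is shown as the alternative.
- Independence of tests is assumed first, then relaxed.

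**Formulas.** With m true nulls tested at level a, the expected number of false positives is m x a. The chance of at least one is 1 - (1 - a)^m.

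| True nulls | Level | Expected false positives | Chance of at least one |
|---|---|---|---|
| All 19 | 0.05 | 19 x 0.05 = 0.95 | 1 - 0.95^19 = 62% |
| 9 (sorafenib targets excluded) | 0.05 | 9 x 0.05 = 0.45 | 1 - 0.95^9 = 37% |
| All 19 | 0.01 | 19 x 0.01 = 0.19 | 1 - 0.99^19 = 17% |
| 9 | 0.01 | 9 x 0.01 = 0.09 | 1 - 0.99^9 = 9% |

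**Correlated tests.** By simulation with all 19 null at 0.05, the chance of at least one false positive is 52% at a common correlation of 0.3 and 41% at 0.5. The expected number stays at 0.95.

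**Power left after adjustment.** As a check stricter than FDR, take Bonferroni over 19 tests: 0.05/19 = 0.00263 per test. Power for a paired change of 1 SD is then 99.99% with 50 pairs, 93% with 25 pairs and 82% with 20 pairs. Participation in ST1 is optional, so the number of pairs may be well below 75. These three values show the range.

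**The case against.** The strongest reply is that section 10.3.4 calls these studies exploratory, the substudy is optional, and no primary or secondary endpoint, stopping rule or treatment decision uses them. Unadjusted p-values in labelled exploratory work are common. This stands, and it limits the point to interpretation. It does not remove it: the gene array is equally exploratory and still gets an FDR assessment.

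A global null is also implausible when 10 of the 19 items are named because they are sorafenib targets. That stands too, and it is why the 37% figure belongs beside the 62%. Six of the remaining nine are only to be considered. Against this, each pathway counts once in the 19 although it covers several proteins.

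The contrast with Core #2 should not be overdrawn. The plan assesses the FDR there but still selects genes at a nominal threshold. The gap is that one platform reports an error rate and the other does not.

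A reader might infer two stronger claims, and the documents support neither.

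1. *That some 300 tests are planned.* The text says that many antibodies are available on the platform, and the biopsy guidelines describe a constrained evaluation of selected pathways. Multiplying 0.05 by 300 describes an analysis that nobody has planned.

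2. *That choosing pathways from gene results in the same biopsies inflates the protein tests well above 5%.* That happens if genes are picked on the direct change from pre-treatment to day 8. The selection written in section 15.3.3 instead compares pre-treatment and day 8 each with normal tissue, and requires both to differ. I simulated that rule with no treatment change: 25 pairs, and as assumptions 20 controls, a tumour-normal shift of 0.5 or 1 SD, pre/post correlation 0 or 0.5, and RNA-protein change correlation 0.2 to 0.6, with the fold criterion not modelled. The protein test rejected in 3% to 5% of selected cases, so there was no inflation. The genetic studies also include exome sequencing, and a pathway chosen on mutations carries no pre/post RNA change. The opening of the Core #2 paragraph is loose enough that a direct contrast cannot be excluded, so a labelling request is justified but an inflation figure is not.

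**Conclusion.** The concern holds in a limited form. Section 15.3.3 has no multiplicity control and no stated test count for the protein comparisons. On the 19 named items, the chance of at least one false positive lies between 37% (9 nulls) and 62% (19 nulls). This rests on an assumed two-sided 0.05 per test and on independence. It is lower with positively correlated tests or a level of 0.01, and higher if the pathways expand into several proteins each. The trial's efficacy and safety conclusions are unaffected. What is affected is how far the list of proteins said to change can be trusted. Severity: minor.

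**What to change.** In section 15.3.3, under Core #3 and 4:
1. Apply Benjamini-Hochberg, or the permutation FDR approach already described for Core #2, across all antibodies actually run, for example at 10%.
2. State the number of antibodies run and the level used.
3. Report antibodies added because of gene results in the same biopsies separately from those already named in section 10.3.4, labelled as not independent confirmation.
4. Correct or remove the 93% power statement, since it does not match a paired t-test in 75 patients.

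If all nulls are true and the tests are independent, Benjamini-Hochberg at 10% holds the chance of any false positive to 10%, against 62% for unadjusted tests on 19 items. If some proteins truly change, it limits the expected share of false entries on the list rather than the chance of any.

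The gene-then-protein sequence in section 10.3.4 need not change. The cost is a few lines in the plan and a standard adjustment in the analysis. The downside is that fewer proteins will be declared changed. The power loss for a 1 SD change is small at 25 pairs or more for a panel of about 19, and grows with fewer pairs or a longer panel.

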### **Core #5**

Biopsies will be descriptive and comment on 1) proliferation (Ki-67 expressed as percentage) to assess treatment response (pre-treatment base line and post therapy for drug effect) and expressed as percentage of tumor cells as <10%, 10-25%, 25-50% and >50%, 2) degree of fibrosis, 3) changes in vascularity, 4) necrosis and 5) ratio of nuclear to cytoplasmic beta catenin.

For TMA construction, the techniques are previously well described by Lazar and colleagues. Hematoxylin and eosin (H&E) stained sections will be reviewed to define areas of desmoid tumor; dermal scars, reactive tissue and solitary fibrous tumor will serve as controls. Using an automated TMA apparatus (ATA-27; Beecher Instruments, Sun Prairie, WI), 0.6-mm punch samples (two per case) will be obtained along with controls and formatted into three recipient blocks. H&E-staining of 4-micron TMA sections will be used to verify all samples.

Immunohistochemistry: The polymeric biotin-free horseradish peroxidase method on a Microsystems Bond Max stainer (Beecher Instruments, Bannockburn, IL) will be used for immunohistochemistry. Four-micron-thick sections will be prepared from formalin-fixed paraffin-embedded tissue blocks and dried in a 60-degree oven for 20 minutes. Sections will be placed in the automated Bond Max stainer, pretreated with enzyme-induced epitope retrieval for 2 minutes followed by incubation with antibodies against beta-catenin (BD Biosciences, San Jose, CA), midkine (Antigenix America, NY), MMP2 (Chemicon, MA) and ADAM12 (Abcam, MA). Additional antibodies may be utilized to interrogate specific pathways identified in micro-array work. Anti-mouse secondary antibody and the Refine polymer detection kit (Leica) will be used for immunostaining, with 3,3-diaminobenzidine serving as chromagen. Positive and negative controls will run in parallel. Labeling intensity grading will be performed by soft tissue pathologist ([name]) as none (\_0), weak (\_1), moderate (\_2), or strong (\_3). For the ratio of cellular to nuclear beta catenins, the percentage of positive tumor cells will be estimated from the two paired TMA samples for each case. For nuclear staining, weak (\_1) will be defined functionally as having to view nuclei at X400 to confirm nuclear accumulation. Moderate (\_2) staining could be viewed at X200 and the blue hematoxylin nuclear counterstain. In strong (\_3) staining, the nuclear counterstain will no longer be visible in the majority of nuclei. The staining on the entire array will be performed in the MSKCC clinical immunohistochemistry facility on two occasions and each scored independently.

### **Plasma and Whole Blood Analysis**

DNA will be extracted from whole blood to serve as normal tissue control for tumor studies outlined under: “core sample #1 and #2– Nucleic acid changes”. In addition, DNA samples will be analyzed for genetic factors contributing to the subject’s response to sorafenib in terms of pharmacodynamics, efficacy and tolerability. Such genetic factors may include genes for drug-metabolizing enzymes, drug transport proteins, genes within the target pathway or other genes believed to be related to drug response. Some genes currently insufficiently characterized or unknown may be understood to be important at the time of analysis. Plasma specimens will be also be utilized to evaluate known and novel markers (peptides/proteins and drug metabolites) of response and/or resistance to disease.

## 11.0 DRUG FORMULATION, AVAILABILITY, AND PREPARATION

### 11.1 General Considerations

Qualified personnel who are familiar with procedures that minimize undue exposure to themselves and to the environment should undertake the preparation, handling, and safe disposal of chemotherapeutic agents in a self-contained, protective environment.

### 11.2 Sorafenib (BAY 43-9006, Nexavar; NSC 724772 / IND #116279) / Placebo

- **Chemical Name** (4-{3-[4-chloro-3-(trifluoromethyl)-phenyl] ureido}-phenoxy)-N2-methylpyridine-2-carboxamide-4-methyl-benzensulfonate.
- **Other Names** BAY 43-9006; Nexavar®; sorafenib; BAY 54-9085 (tosylate salt)
- **Classification** Multi-kinase inhibitor
- **Molecular Formula** C12H16ClF3N4O3 X C7H8O3S M.W.: 637 [g/mole]
- **Description** Round, red 10 mm tablets
- **How Supplied** Sorafenib tosylate is supplied by Bayer Healthcare AG and distributed by the DCTD, and available as 200mg coated tablets. The inactive ingredients are microcrystalline cellulose, croscarmellose sodium, hydroxypropylmethyl cellulose, magnesium stearate, sodium lauryl sulfate, and a film coat with hydroxypropylmethylcellulose, polyethylene glycol, titanium dioxide and red iron oxide. The 200 mg tablets are packaged in HDPE bottles containing 140 tablets.

#### 11.2.1 Availability

Sorafenib and matching Placebo will be provided free of charge by Bayer Pharmaceuticals and distributed by the Pharmaceutical Management Branch (PMB), Cancer Therapy Evaluation Program (CTEP), Division of Cancer Treatment and Diagnosis (DCTD), National Cancer Institute (NCI).

Sorafenib and matching Placebo are supplied as an immediate-release, film-coated, round, red-colored tablet for oral administration. Each Sorafenib tablet contains 200 mg of the free base (i.e., BAY 43-9006). The Sorafenib and Placebo tablets contain croscarmellose sodium, microcrystalline cellulose, hydroxypropylmethylcellulose, sodium lauryl sulfate, and magnesium stearate. For Sorafenib and Placebo, the film coat consists of hydroxypropylmethyl cellulose, polyethylene glycol, titanium dioxide and red iron oxide. The film coating has no effect on the rate of release of the active sorafenib.

Each tamper-evident, child-resistant, opaque, high-density polyethylene (HDPE) bottle contains 140 tablets of Sorafenib 200 mg or matching Placebo.

**No open-label starter supplies will be available for this study.** Initial open-label, patient-specific clinical supplies of sorafenib will be shipped from the Pharmaceutical Management Branch (PMB) to the registering investigator at the time of patient randomization and should arrive within 7 to 10 days of randomization (see Section 11.2.9)

For **BLINDED (sorafenib or placebo) THERAPY**, each bottle will be labeled with...

- the protocol number (i.e., "A091105")
- the bottle number (i.e., "Bottle 1 of 1")
- the number of tablets (i.e., "140 tablets")
- the patient ID number (e.g., "999999", where "999999" represents a unique patient identifier assigned by ALLIANCE at registration).
- the patient initials (i.e., last initial, first initial, middle initial [e.g., "L, FM"])

- the agent identification (i.e., “Sorafenib 200 mg or Placebo”)
- a blank line for the pharmacist to enter the patient’s name
- administration instructions (i.e., “Take \_\_\_ tablets once daily.”)
- storage instructions (i.e., “Store at controlled room temperature, not to exceed 25°C (77°F).”)
- emergency contact instructions
- a Julian date

For **CROSSOVER (open label sorafenib) THERAPY**, each bottle will be labeled with ...

- the protocol number (i.e., “A091105”)
- the bottle number (i.e., “Bottle 1 of 1”)
- the number of tablets (i.e., “140 tablets”)
- the patient ID number (e.g., “999999”, where “999999” represents a unique patient identifier assigned by ALLIANCE at registration)
- the patient initials (i.e., last initial, first initial, middle initial [e.g., "L, FM"])
- the agent identification (i.e., “Sorafenib 200 mg)
- a blank line for the pharmacist to enter the patient’s name
- administration instructions (i.e., “Take \_\_\_ tablets once daily.”)
- storage instructions (i.e., “Store at controlled room temperature, not to exceed 25°C, 77°F.”)
- emergency contact instructions
- a Julian date

The Julian date indicates the day the bottle was labeled and shipped and is composed of the last two digits of the calendar year (e.g., 2013 = 13, 2014 = 14) and a day count (e.g., January 1 = 001, December 3 = 365). For example, a bottle labeled and shipped on January 1, 2013 would have a Julian date of ‘13001’ and a bottle labeled and shipped on December 31, 2014 would have a Julian date of ‘14365’. The Julian date will be used by PMB for recalls. When a lot expires, PMB will determine the last date the expired lot was shipped and will recall all bottles (i.e., both Sorafenib and Placebo) shipped on or before that date thus eliminating any chance of breaking the blind.

**Questions about drug orders, transfers, returns, or accountability should be addressed to the PMB by calling [contact] Monday through Friday between 8:30AM and 4:30PM Eastern Time.**

